15.2.1.2 WHOQoL-BREF

The WHOQoL-BREF questionnaire (WHO 1996) assesses the individual's perceptions in the context of their culture and value systems, and their personal goals, standards and concerns. It comprises 26 items, which measure the following broad domains: physical health (items 3, 4, 10, 15, 16, 17 and 18), psychological health (items 5, 6, 7, 11, 19 and 26), social relationships (items 20, 21 and 22), and environment (items 8, 9, 12, 13, 14, 23, 24 and 25). There are also 2 items that are examined separately: item 1 asks about individual overall perception of quality of life and item2 asks about individual overall perception of their health.

Domain scores are scaled in a positive direction (i.e. higher scores denote higher QoL). The scores of items 3 ("To what extent do you feel that physical pain prevents you from doing what you need to do?"), 4 ("How much do you need any medical treatment to function in your daily life?") and 26 ("How often do you have negative feelings such as blue mood, despair, anxiety, depression?"), which are negatively phrased, will be reversed.

Document:	Y:\Kimberly-Clark\DryNites\Documentation\SAP\DryNites_SAP_v1.0_20200203		
Author:	[name]	Version Number:	1.0
		Version Date:	03Feb2020
Template No.:	RWI_TP_BIOS0013 Revision 1		Reference: RWI_WI_BIOS0015
Effective Date:	15Jun2018		

The mean score of items within each domain will be used to calculate the domain scores. The mean will be then multiplied by 4 as to be directly comparable with scores derived from the WHOQOL-100. As last steps, the data transformation reported below will be applied to obtain a 0-100 score:

- Domain 1 to 4: (domain score 4)*100/16;
- Item 1 and 2: (items score -1)*100/4.

Higher scores denote higher QoL.

Where more than 20% of data is missing from an assessment, the assessment should be discarded. Where an item is missing, the mean of other items in the domain is substituted to the missing item score. Where more than 2 items are missing from the domain, the domain score should not be calculated (except for domain 3 [Social relationships], where the domain should only be calculated if <1 item is missing).

The 3 questions added at the end of the questionnaires will be listed only.

15.2.1.3 PDSS

The PDSS questionnaire (Drake et al. 2003) has been developed to measure daytime sleepiness of middle-school children and examine the relationship between daytime sleepiness and school-related outcomes.

It consists of 8 items assessing daytime sleepiness and rated on a 5-point Likert scale ranging from 4 (Always/ Very often) to 0 (Never); the score of the third item ("Are you usually alert most of the day?") will be reversed to calculate the total score as the sum of single items score. Higher scores

Document:	Y:\Kimberly-Clark\DryNites\Documentation\SAP\DryNites_SAP_v1.0_20200203		
Author:	[name]	Version Number:	1.0
		Version Date:	03Feb2020
Template No.: F	RWI_TP_BIOS0013 Revision 1		Reference: RWI_WI_BIOS0015
Effective Date:	15Jun2018		

indicate greater daytime sleepiness, and were associated with reduced total sleep time, poorer school achievement, poorer anger control, and frequent illness.

15.2.1.4 CIS

The CIS (Bültmann et al. 2000) is a 20-item fatigue questionnaire for which the person indicates on a 7-point scale to what extent the particular statement applies to him or her and it measures 4 dimensions of fatigue: fatigue severity (items 1, 4, 6, 9, 12, 14, 16, 20), concentration problems (3, 8, 11, 13, 19), reduced motivation (2, 5, 15, 18) and activity (7, 10, 17). Each domain score is calculated as the sum of items included in the domain. The CIS total score can be calculated by adding the 4 dimensions.

15.2.1.5 Absorbent Pants and DryNites® Clinical Trial Questionnaires

The child and parents'/carers' perspectives on their experience with previous absorbent pants/nappies, and on the attributes of DryNites® vs. previously used products will be recorded via 2 specific questionnaires designed for this study and administered at study entry (Absorbent Pants Clinical Trial Questionnaire, about previous products) and at Day 28 ± 7 (DryNites® Clinical Trial Questionnaire).

Each questionnaire includes the following: identification of previous absorbent product (question 1), 2 narrative questions, 11 statements about the absorbent product (responses: Agree, Tend to agree, Neither agree or disagree, Tend to disagree, Disagree). The Absorbent Pants Clinical Trial Questionnaire includes 6 questions on the attributes of the previous absorbent product, responded on a 1-10 scale (with 1= not at all, and 10 being the highest level of appreciation). The DryNites®

Document:	Y:\Kimberly-Clark\DryNites\Documentation\SAP\DryNites_SAP_v1.0_20200203		
Author:	[name]	Version Number:	1.0
		Version Date:	03Feb2020
Template No.: F	RWI_TP_BIOS0013 Revision 1		Reference: RWI_WI_BIOS0015
Effective Date:	15Jun2018		

Questionnaire includes an overall preference question, responded on a 1-10 scale, and 8 specific questions on preference for DryNites® attributes compared to the previous absorbent product.

15.2.2 Missing Data Methods for Secondary Variables

No reliable methods are proposed to manage missing data in PinQ, PDSS and CIS. Please see Section 15.2.1.2 for instruction on missing management for WHOQoL-BREF.

Total scores and the domain scores (applicable for PinQ and CIS only) will be calculated in case of at least 50%+1 of questions completed and the subscale score will be prorated by multiplying the sum of the subscale by the number of items in the subscale, then dividing by the number of items actually answered. The results obtained will be presented along with results obtained without missing substitution.

No missing substitutions will be applicable on Absorbent Pants and DryNites® Clinical Trial Questionnaires.

15.2.3 Analysis of Secondary Variables

15.2.3.1 Analysis of Secondary Variables

Analyses of PinQ, WHOQoL-BREF, PDSS and CIS questionnaires will be provided by group on the Randomised Set.

Frequency distribution and descriptive statistics, when applicable, will be provided by visit for each item of questionnaires, while summary statistics for total scores, domain scores and changes from baseline will be provided as applicable.

The effect size will be also presented as descriptive statistics of ratio between the change from baseline and baseline SD.

Document:	Y:\Kimberly-Clark\DryNites\Documentation\SAP\DryNites_SAP_v1.0_20200203		
Author:	[name]	Version Number:	1.0
		Version Date:	03Feb2020
Template No.: F	RWI_TP_BIOS0013 Revision 1		Reference: RWI_WI_BIOS0015
Effective Date:	15Jun2018		

The percentage of patients with change from baseline ≥ 0.5 time the baseline SD will be also provided.

For applicable questionnaires an ANCOVA with baseline PROs value as covariate will be performed. Group comparisons will be performed for the difference in least squares means (LSMean) at Visit 3. The LSMean (standard error [SE]) by group and visit (if applicable), the LSMean difference between groups, along with 95% confidence limits of the group differences and the p-value for the group comparison will be displayed as purely exploratory. For the change from baseline, p-value for the within-group difference will also be displayed as purely exploratory. The Absorbent Pants Clinical Trial Questionnaire administered at study entry, and the DryNites® Clinical Trial Questionnaire administered at the end of the run-in period, will be analysed descriptively for the Screened Set.

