# 4.5.2.1. Paediatric Incontinence Questionnaire (PinQ)

The PinQ will be used to assess the child's QoL. The PinQ is a validated cross-cultural continence-specific paediatric QoL questionnaire to assess children with bladder dysfunction, developed by Bower et al. (Bower et al. 2006). It is available as self-rated and proxy versions. This will be completed by the child themselves in the older participant group and will be completed by the parent/carer on behalf of the child in the younger participant group.

The PinQ measures the emotional impact that urinary incontinence has on a child. It consists of 20 urinary incontinence QoL related questions divided in 2 dimensions: intrinsic (14 items) and extrinsic (6 items), which are graded on a scale of 0 to 4 (0=No, 1=Hardly ever, 2=Sometimes, 3=Often, 4=All the time) with a total possible global score of 80.

The total score indicates the impact urinary incontinence has on the child's QoL with the higher scores indicating a more significant effect.

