# 4.5.2.3. Paediatric Daytime Sleepiness Scale (PDSS)

The PDSS questionnaire will be used to assess the child's sleep. It is comprised of 8 items assessing daytime sleepiness and rated on a 5-point Likert scale ranging from 4 (Always/Very often) to 0 (Never); the score of the third item needs to be reversed to calculate the total score. Higher scores indicate greater daytime sleepiness, and were associated with reduced total sleep time, poorer school achievement, poorer anger control, and frequent illness. The scale score is correlated with total hours of night-time sleep (Drake et al. 2003). While no time reference is specifically identified by the questionnaire, items query feelings of drowsiness in a variety of settings over the course of the day. It is validated for administration in children 5-17 years old. This will be completed by the child themselves (with attendance of an adult) in the older participant group and will be completed by the parent/carer on behalf of the child in the younger participant group.

At enrolment, the site will record whether the child takes regular daytime naps; these children will be excluded from the analyses of sleep.

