7.4 Common Calculations

For quantitative measurements, change from baseline will be calculated as:

(Test Value at Visit X – Baseline Value).

The effect size will be calculated as:

[(Test Value at Visit X – Baseline Value)/ Baseline SD].

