15.2.1 Secondary Variables & Derivations

15.2.1.1 PinQ

Effective Date: 15Jun2018

The PinQ (Bower et al. 2006) measures the emotional impact that urinary incontinence has on a child. It consists of 20 urinary incontinence QoL related questions which are graded on a scale of 0–4 (0=No, 1=Hardly ever, 2=Sometimes, 3=Often, 4=All the time) with a total possible score of 80.

Document:	Y:\Kimberly-Clark\DryNites\Documentation\SAP\DryNites_SAP_v1.0_20200203		
Author:	[name]	Version Number:	1.0
		Version Date:	03Feb2020
Template No.:	RWI_TP_BIOS0013 Revision 1		Reference: RWI_WI_BIOS0015

Two factors scores cast the items from the children's questionnaires into 2 groups, which could be considered as extrinsic (items 2, 3, 6, 12, 16 and 20) and intrinsic (items 1, 4, 5, 7, 8, 9, 10, 11, 13, 14, 15, 17, 18, 19, 20) impact. Intrinsic items generally related to how the child felt or what they believed, whilst the extrinsic items were more likely to relate to external limitations imposed by urinary symptoms.

The factor score will be obtained as the sum of items included in each factor and the total score will be calculated as the sum of each single non-missing score. Scores will indicate the impact urinary incontinence has on the child's QoL with the higher score indicating a more significant effect.

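### One signed 0.5 SD threshold is applied to four questionnaires that score in opposite directions, so the percentage counts worsening on some and improvement on another

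*SAP*

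**What the plan says.** SAP 15.2.3.1 covers all four instruments together: "Analyses of PinQ, WHOQoL-BREF, PDSS and CIS questionnaires will be provided by group on the Randomised Set". It then sets one threshold for them: "The percentage of patients with change from baseline" of at least 0.5 times the baseline SD. Protocol 5.4.2 and the synopsis carry the same one-signed rule, but name an SD without saying that it is the baseline SD.

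The sign comes from SAP 7.4: "For quantitative measurements, change from baseline will be calculated as" the value at the visit minus the baseline value. A positive change is a score that went up.

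The directions of the scales are given separately:

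- **PinQ.** Protocol 4.5.2.1 describes the total as the impact of incontinence on the child's QoL, "with the higher scores indicating a more significant effect"; SAP 15.2.1.1 says the same.
- **PDSS.** Protocol 4.5.2.3: "Higher scores indicate greater daytime sleepiness". SAP 15.2.1.3 agrees.
- **CIS.** No direction is stated as a scoring rule. Protocol 4.5.2.4 gives a cut-off of 35 on the fatigue severity subscale for severe fatigue, and 76 on the CIS for risk of sick leave or work disability. Both imply that higher is worse.
- **WHOQoL-BREF.** Protocol 4.5.2.2 and SAP 15.2.1.2 both say that higher scores mean better QoL.

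The secondary objectives for all four (SAP 3.2, Protocol Table 1) ask whether using DryNites improves the outcome compared with not using absorbent pants.

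**The concern.** A threshold percentage is read as a count of patients who did well or of patients who did badly. Here it is neither consistently. The same rule picks out one kind of patient on three instruments and the other kind on the fourth, and nothing in the documents labels which is which. If an arm fares better on every questionnaire, its percentage would tend to be lower on PinQ, PDSS and CIS and higher on WHOQoL-BREF. Someone comparing the arms across these tables could see a conflict in data that agree. It is also the SAP's only summary of these scores that applies a threshold patient by patient.

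**Working it through.** The plan states no expected value for this percentage, so there is no figure to reproduce. The check is first of the sign, then of the size under stated assumptions.

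**Step 1: sign by instrument.** The rule counts a patient if (visit − baseline) ≥ +0.5 × baseline SD.

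| Instrument | Higher score means | Patient counted by the rule |
|---|---|---|
| PinQ | worse (stated) | worsened |
| PDSS | worse (stated) | worsened |
| CIS | worse (inferred from cut-offs) | worsened |
| WHOQoL-BREF | better (stated) | improved |

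For example, take PinQ with an assumed baseline SD of 12. A child going from 40 to 30 has −10/12 = −0.83 SD, an improvement, and is not counted. A child going from 40 to 50 has +0.83 SD, a deterioration, and is counted.

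**Step 2: is the sign set elsewhere?** Protocol 5.4.2, the synopsis, SAP 7.4 and SAP 15.2.3.1 neither take an absolute value nor reverse the sign by instrument, and none labels the result as improvement or worsening.

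**Step 3: size on a higher-is-worse scale (illustration).** The documents give no mean or SD of change. Assume change divided by baseline SD is normal with mean m and SD s = √(2(1 − ρ)), where ρ is the correlation between visits and the SD is the same at both. Then ρ = 0.5 gives s = 1, so the SD of change equals the baseline SD, and ρ = 0.7 gives s = √0.6 = 0.775.

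- Counted by the rule: 1 − Φ((0.5 − m)/s)
- Improved by at least 0.5 SD: Φ((−0.5 − m)/s)

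At m = −0.5 and s = 1, the rule counts 1 − Φ(1) = 15.9%, and Φ(0) = 50.0% improved.

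| Mean change m (SD units) | Counted by rule, ρ 0.5 / 0.7 | Improved ≥0.5 SD, ρ 0.5 / 0.7 |
|---|---|---|
| −0.8 (improvement) | 9.7% / 4.7% | 61.8% / 65.1% |
| −0.5 (improvement) | 15.9% / 9.8% | 50.0% / 50.0% |
| 0 | 30.9% / 25.9% | 30.9% / 25.9% |
| +0.5 (worsening) | 50.0% / 50.0% | 15.9% / 9.8% |

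The two counts agree only when the mean change is zero.

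**Step 4: the flip between instruments.** Suppose the stopping arm worsens by 0.5 SD on every instrument and the continuing arm does not change. At ρ = 0.5 the rule shows, on PinQ, 50% (stopping) against 31% (continuing). On WHOQoL-BREF, where worsening is a fall in score, it shows 16% (stopping) against 31% (continuing). The data are consistent, yet the ordering of the arms reverses.

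**Step 5: would an absolute-change reading help?** It is not what is written. It would give 65.9% (ρ 0.5) or 59.8% (ρ 0.7) for a 0.5 SD mean improvement and exactly the same for a 0.5 SD mean worsening, so it could not show benefit.

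**The case against.** A reader might infer that for three of the four instruments the table answers the opposite of the study question, and that the better arm would be presented as having the poorer response. The documents do not support that, for four reasons.

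- **No response label.** Neither document calls the figure a response or an improvement rate. The defect is an unlabelled, inconsistent direction and not a reversed result.
- **Worsening is a relevant outcome here.** Protocol Table 2 and section 4.7.3 place the QoL and sleep questionnaires at Visit 2, after four weeks of DryNites in every child. Protocol 4.5.2 also lists Day 0, but SAP 7.2 takes the last measurement up to randomisation as baseline. One arm then continues and the other stops. A benefit of continued use could therefore appear mainly as worsening in the arm that stops, and on PinQ and PDSS the rule captures that. Only on WHOQoL-BREF would it then miss the patients of interest.
- **Little rests on the figure.** Protocol Table 1 lists changes in scores as the endpoints, not this percentage. SAP 8.1 plans no confirmatory testing. Signed changes, effect sizes and least squares mean differences with 95% limits are reported for the same scores.
- **The output templates are not visible.** SAP 9 says that templates describe the format and content of the outputs, and they might state a direction.

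The first three points stand and limit the consequence. They do not remove the inconsistency: if worsening is wanted, the rule is wrong for WHOQoL-BREF; if improvement is wanted, it is wrong for the other three. The fourth limits certainty about the final tables, but a template cannot be assumed to correct a rule written in the SAP. The CIS direction is indeed an inference, and the cut-offs speak only to fatigue severity and the CIS as a whole; that is a reason to state it.

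**Conclusion.** The point holds as an inconsistent rule. Followed literally, the planned percentage counts worsening on PinQ and PDSS, worsening on CIS by inference, and improvement on WHOQoL-BREF. On a higher-is-worse scale with a true mean improvement of 0.5 SD it would show about 10–16% when 50% improved by that much; with a mean worsening of 0.5 SD it would show 50%, all of them worsened. These sizes rest on normal change, equal SDs at both visits and an assumed correlation of 0.5 to 0.7. The direction of the flip does not depend on them, although the CIS row depends on the inferred scoring. The effect is confined to a descriptive secondary summary. The primary equivalence analysis and the ANCOVA are untouched. It is a small correction worth making before the tables are produced.

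**What to change.** In SAP 15.2.3.1:

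- Define improved as change ≤ −0.5 baseline SD for PinQ, PDSS and CIS, and ≥ +0.5 baseline SD for the WHOQoL-BREF domains. Define worsened as the mirror image, and unchanged as everything between.
- Tabulate improved, unchanged and worsened by arm for each score. This serves both readings: benefit from continuing and harm from stopping.
- State the CIS direction explicitly, for each subscale and the total.

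The protocol carries the same rule, so either amend Protocol 5.4.2 and the synopsis to match, including naming the baseline SD, or record the change in SAP 4.3.

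The cost is a few sentences in the SAP, the protocol alignment or the SAP 4.3 entry, and trivial programming. No new data are needed.

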15.3 Exploratory Analysis

Effective Date: 15Jun2018

The exploratory analysis will include the refresh of the analysis on patient disposition, primary and secondary analysis and adverse events, including the data collected over the extension period. A repeated measure model will be presented to assess the extension period effects on PinQ, WHOQoL-BREF, PDSS and CIS questionnaires.

Repeated measure model will be handled with mixed effects models using SAS PROC MIXED with an unstructured correlation matrix to model the within-patient errors, unless the model does not converge, in which case the heterogeneous Toeplitz covariance structure followed by the heterogeneous first-order autoregressive covariance structure will be checked. Parameters will be estimated using the Newton-Raphson algorithm. Denominator degrees of freedom will be estimated

Document:	Y:\Kimberly-Clark\DryNites\Documentation\SAP\DryNites_SAP_v1.0_20200203		
Author:	[name]	Version Number:	1.0
		Version Date:	03Feb2020
Template No.:	RWI_TP_BIOS0013 Revision 1		Reference: RWI_WI_BIOS0015

using the Kenward-Roger approximation by fitting values from post-randomisation scheduled visits. This likelihood-based approach is tolerant of missing data provided that they are MAR. Missing at random assumes that the missing values are systematically related to other, measured covariates and that no unmeasured related covariates exist.

16. SAFETY OUTCOMES

All outputs for safety outcomes will be based on the Safety Analysis Set.

16.1 Adverse Events

Adverse Events (AEs) will be coded using the version of MedDRA available at the time of the analysis.

Treatment emergent adverse events (TEAEs) are defined as AEs that first occurred or worsened in severity after the start of screening period and prior to the end of the extension period.

See Appendix 1 for handling of partial dates for AEs. In the case where it is not possible to define an AE as treatment emergent or not, the AE will be classified by the worst-case scenario; i.e. treatment emergent.

The AEs that occurred from ICF signature till randomisation will be described separately and presented in a listing.

For each group, numbers and proportion of TEAEs, device-related TEAE and serious TEAEs will be tabulated by SOC and PT along with number of events.

Medical Device Incidents (MDI) not associated with a TEAE will be described separately in a listing.

Document:	Y:\Kimberly-Clark\DryNites\Documentation\SAP\DryNites_SAP_v1.0_20200203		
Author:	[name]	Version Number:	1.0
		Version Date:	03Feb2020
Template No.: I	RWI_TP_BIOS0013 Revision 1		Reference: RWI_WI_BIOS0015

Effective Date: 15Jun2018

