## 5.4.4. Safety Analyses

All safety analyses will be performed on the Safety Analysis Set.

AEs are reported since ICF signature, throughout the patients' discontinuation of the study.

Treatment-emergent adverse events (TEAEs) are defined as AEs that first occurred or worsened in severity after randomisation and prior to the end of the extension period.

AEs that occurred from ICF signature till randomisation will be described separately.

AEs will be coded using MedDRA. For each group, numbers and proportion of TEAEs, device-related TEAE and serious TEAEs will be tabulated by SOC and PT.

Medical Device Incidents not associated with a TEAE will be described separately.

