4.3 Changes to Analysis from Protocol

Concomitant medications will be collected in relation to adverse events and medical device incidents only. For this reason, the summary of concomitant medication will be provided on randomised analysis set only as no data will be collected for patients screened and not randomised.

Document:	Y:\Kimberly-Clark\DryNites\Documentation\SAP\DryNites_SAP_v1.0_20200203		
Author:	[name] Version Number:		1.0
		Version Date:	03Feb2020
Template No.: RWI_TP_BIOS0013 Revision 1			Reference: RWI_WI_BIOS0015
Effective Date: 15Jun2018			

Safety set definition will be modified to include all patients exposed to DryNites for at least 1 night after signature of informed consent.

Treatment emergent adverse events will be defined as all events occurred or worsened in severity after the start of the screening period.

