6.3 Safety Analysis Set

The safety analysis set (SAF) will contain all patients exposed to DryNites® for at least 1 night after signature of informed consent.

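### The SAP counts treatment-emergent events from screening, so run-in events on DryNites enter the no-pants column and the between-group ratio is compressed

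*SAP*

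**What the plan says.** - **TEAE window, SAP.** Section 16.1 defines TEAEs as "AEs that first occurred or worsened in severity after the start of screening period", with the end of the extension as the upper limit. Section 4.3 declares this as a change from the protocol: "Treatment emergent adverse events will be defined as all events occurred or worsened in severity after the start of the screening period". The Appendix 1 rows for a known start date agree: onset from the screening date to the end of the extension makes the event a TEAE.
- **TEAE window, protocol.** Section 5.4.4 has "AEs that first occurred or worsened in severity after randomisation and prior to the end of the extension period", with earlier events described separately.
- **Tabulation.** SAP 16.1: "For each group, numbers and proportion of TEAEs, device-related TEAE and serious TEAEs will be tabulated by SOC and PT". Section 16.1.1 counts repeat events once within a SOC or PT. The SAP states no split by study period and no table limited to events after randomisation. Pre-randomisation events are also to be described separately, in a listing.
- **Safety set.** SAP 6.3 takes every child exposed to DryNites "for at least 1 night after signature of informed consent", which includes children who were never randomised. Protocol 5.3, Table 4, sets the safety set equal to the Randomised Set.
- **Exposure.** SAP 4.1 assigns all participants to DryNites every night of the 4-week run-in and then randomises 2:1 to stop or continue.
- **Causality.** Protocol 7.1.5 asks for relationship to DryNites in the run-in and, afterwards, in the continuation group only. It is not applicable in the group that stops.

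**The concern.** Randomisation separates the arms only from Visit 2 onwards. Before that, both arms have the same exposure to the same device. A by-group table that starts at screening therefore adds a shared 4-week block of DryNites exposure to both columns, and the no-pants column no longer describes children without pants.

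Protocol section 2 says that the side-effects of DryNites have not been evaluated in any study. The by-arm safety table is the only randomised view of tolerability that this trial offers, so what it measures should be clear. Someone comparing the two columns as DryNites against no DryNites would read the wrong ratio.

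**Working it through.** The documents give no adverse event rate, safety hypothesis or safety sample size, so there is no plan figure to reproduce. Event rates below are assumptions.

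**Inputs from the documents.** Three periods of 4 weeks (SAP 4.1); 2:1 allocation (SAP 4.1); about 120 randomised (protocol 4.3), hence 80 stopping and 40 continuing.

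**Model.** Constant event rates per child per 4 weeks: D on DryNites, N off. Risk = 1 − exp(−cumulative rate). The continuing arm has rate D throughout. The stopping arm has rate D in the run-in and N afterwards.

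**1. Share of the window.** The run-in is 28/56 days = 50% of the TEAE window at the core analysis and 28/84 = 33% with the extension.

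**2. Device event, 5% risk per 4 weeks on DryNites, 0% off.**
- Core period, from randomisation: 5% v 0%, difference 5.0 points, about 2/40 v 0/80 children.
- Core period, from screening: 1 − 0.95² = 9.75% v 5.0%. The ratio is 9.75/5.0 = 1.95 and the difference 4.75 points, about 3.9/40 v 4.0/80 children.
- If all children enter the extension, from screening: 1 − 0.95³ = 14.3% v 5.0%, a ratio of about 2.9.
- At 10% risk, core period: 1 − 0.90² = 19% v 10%, instead of 10% v 0%. The difference is 9 points instead of 10.

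**3. General result, with true rate ratio r = D/N.**
- Apparent core rate ratio = 2D/(D + N) = 2r/(r + 1), below 2 for any r. For r = 1.5, 2 and 3 it is 1.20, 1.33 and 1.50.
- With the extension it is 3r/(r + 2), below 3. For the same r it is 1.29, 1.50 and 1.80.
- Share of the stopping arm's core-period events that come from the run-in = r/(r + 1): 60%, 67% and 75%.
- The risk difference is multiplied by exp(−D), which is 1 minus the 4-week risk on DryNites: 0.95 at 5%, 0.90 at 10%.
- The expected difference in events per child is unchanged: (D + D) − (D + N) = D − N.

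**4. With background events in both arms.**

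| Assumption | From randomisation | From screening |
|---|---|---|
| Core, no-pants risk 10%, r = 2 | 19.0% v 10.0%; ratio 1.90; difference 9.0 points | 34.4% v 27.1%; ratio 1.27; difference 7.3 points |
| Core, no-pants risk 15%, r = 3 | 38.6% v 15.0%; ratio 2.57; difference 23.6 points | 62.3% v 47.8%; ratio 1.30; difference 14.5 points |
| Risk ratio, core, no-pants risk 5–15%, r 1.5–3 | 1.44–2.85 | 1.16–1.43 |
| Risk ratio, same range, all in extension | 1.39–2.72 | 1.20–1.63 |

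**5. Device-related TEAEs.** Under protocol 7.1.5 the investigator does not rate relationship in the no-pants arm after randomisation. Any investigator-rated device-related TEAE in that column must therefore come from the run-in. One qualification: SAP 16.1.1.2 counts a missing relationship as related, so a blank field after randomisation could add to the column. The 0/80 in step 2 assumes that this does not happen.

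**6. Appendix 1 against itself.** A run-in event with a full start date is a TEAE. A run-in event with a partial date that cannot fall on or after randomisation is classed as not a TEAE. If the partial date could also fall on or after screening, it fits a second row, which makes it a TEAE when its stop date is on or after screening. Precision of the date, rather than timing, then decides the class.

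**The case against.** **The text can be read another way.** SAP 16.1 lists pre-randomisation events separately just before the by-group sentence. The protocol uses the same device to keep them out of the TEAE tables, and one Appendix 1 row points the same way. That makes this a conflict to reconcile. It does not overturn the literal reading: the definition and the change declared in SAP 4.3 make run-in events TEAEs, and a listing does not remove them from a table.

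**The table templates are not in these documents.** SAP section 9 leaves format and content to them, and section 16.1 says group without spelling out randomised arm. Period columns or a column for non-randomised children may exist. Where those children are shown therefore cannot be settled here. The stated rule still needs to be explicit.

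**The change is declared and safety is descriptive.** SAP 3.4 sets only descriptive safety objectives, 8.1 plans no confirmatory testing, and starting the count at device exposure is reasonable for a whole-exposure summary. A reader might infer that the tables are invalid. The documents do not support that: such tables can describe all on-study events.

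**The information is not lost.** SAP 7.1 puts the randomisation date in every listing with an event date, so a reader can split the periods by hand.

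**The size is assumed, and counts may be small.** A reader might also infer that a real device effect would vanish. The working does not show that. The ratio is compressed, but at low event risk the risk difference barely changes, and the expected difference in events per child does not change at all. At 5% risk the contrast from randomisation is about 2 children against 0, and SAP 16.1.1.2 gives only a listing below 5 events.

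**Conclusion.** The point holds as a conflict between documents that affects what the by-group safety tables mean. On the literal SAP text, run-in events on DryNites enter the no-pants column. This disagrees with protocol 5.4.4, with protocol Table 4 and with one row of the SAP's own Appendix 1.

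The consequence is mainly on the ratio scale. The apparent core rate ratio cannot exceed 2 (or 3 with full extension uptake), whatever the true ratio. At an assumed 5% device risk on DryNites and 0% off, 5% v 0% becomes 9.8% v 5.0%, with the risk difference going from 5.0 to 4.75 points. The difference shrinks appreciably only when events are common, as the table shows. The direction of the ratio effect needs only that event rates differ on and off DryNites. The sizes rest on assumed rates, a constant-rate model and, for the extension figures, every child entering it.

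This should be corrected before the safety tables are produced. It does not touch the primary analysis.

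**What to change.** - Restrict by-arm adverse event tables to randomised children and to events with onset or worsening on or after randomisation. SAP 7.2 already treats events starting on the randomisation day as post-baseline.
- Show run-in events for all exposed children, including those never randomised, in a separate single-column table. This keeps the full device exposure that the SAP change set out to capture.
- Align SAP 4.3, 6.3, 16.1 and all rows of Appendix 1 with protocol 5.3 and 5.4.4, so that one window and one safety population apply to each table.

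The cost is SAP wording and a period flag derived from the randomisation date and the event dates already collected under protocol 7.2. No new data are needed.
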